14.0 Statistical Considerations

14.1 Data Analysis Plan: 200 primary participants, including 100 females and 100 males. Within each group there will be 50 early and 50 late puberty participants.

Study Design. This randomized control study will assign study participants into one of four conditions: Close friend both tested, Unfamiliar Peer both tested, Received support from close friend who is not tested, and no partner. To perform the randomization, participants will first be placed into one of four groups based on sex and pubertal stage: early puberty, female;

PROTOCOL TITLE: Does Social Buffering Continue to be Effective Over the Peripubertal Period
When Friends Share the Stressor Experience?

VERSION DATE: v.3.3 3.31.23

late puberty, female; early puberty, male; and late puberty, male. Next, participants within a group will be randomly assigned to one of four conditions equally in order to have a balanced design. Pubertal stage will then be treated as a continuous variable.

Statistical Methods

Preliminary Analyses to Determine Covariates Need for Primary Analyses. The purpose of collecting data on potential covariates is to identify variables that are correlated with both the independent variable (social buffering condition, sex, pubertal stage) and the primary outcome measures. Those covariates that are associated with the independent and outcome variables will be controlled for in the primary analyses. Those that are not will be used to describe the sample, but will not need to be included in the analyses to obtain unbiased estimates. For each potential covariate (listed as “other type” in section 4.3, Outcome Variables), we will conduct correlations or t-tests with pubertal stage, and t-tests, ANOVAs, or chi-square tests (as appropriate) with sex and condition. If data do not confirm to modeling assumptions, we will use non-parametric analogs instead.

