14.2 Power Analysis: For the power analysis for the primary analyses, we calculated the minimum detectable effect size (MDES) assuming $n = 200$, $\alpha = .05$, and power = .80 with a conservative estimate of 12 covariates in our model (see section 4.3). Power was calculated in R (R Core Team, 2018) using the pwr library (Champely, 2018). A power analysis was performed to quantify the MDES (measured as f^2) for a three-way interaction between the social buffering condition, sex, and pubertal stage within a multiple regression model controlling for all potential covariates, two-way interactions, and main effects (the most complex model considered in our primary analysis, see equation 1 below). Assuming these conditions, we should be able to detect an f^2 of 0.056. In other words, adding the three-way interaction to a model containing the covariates and all lower order interactions and main effects, the three-way interaction would need to explain an additional 5.6% of the variability to be detected. This falls between Cohen’s criteria for a small ($f^2 = .02$) and medium-sized effect ($f^2 = .15$) (Cohen, 1988). With a sample size of 200, even if we lost 40 of the participants, assuming all the previous conditions except a sample size of 160, we would still be power enough to detect an f^2 of .070, or still within a small-medium effect size. As the number of covariates decreases, the size of the MDES will decrease. Therefore, this represents a conservative estimate of power for our primary analyses as we are likely to have fewer covariates in our models and will use multiple imputation to correct for missing data. For the two-way interaction and main effects models, described below, the power will be larger than these reported values as the

PROTOCOL TITLE: Does Social Buffering Continue to be Effective Over the Peripubertal Period
When Friends Share the Stressor Experience?

VERSION DATE: v.3.3 3.31.23

models will be simpler. In addition, we ran a power analysis that corrected for multiple comparisons using the conservative Bonferroni's adjustment. Because we expect to run 9 independent multiple regression models or fewer, we ran our models assuming an alpha of 0.05 / 9. Based on this reduced alpha, we expect to be able to detect an effect of .07.

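### Section 14.2: the Bonferroni detectable effect of .07 does not fit with the stated .056; at alpha .05/9 it is about .088 to .10, and power at .07 is 57% to 66%, not 80%

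*Combined protocol and SAP*

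**What the plan says.** Section 14.2 computes a minimum detectable effect, measured as f², "for a three-way interaction between the social buffering condition, sex, and pubertal stage within a multiple regression model". The inputs are n = 200, alpha .05, power .80 and 12 covariates, and the software is the R package pwr. The section reports three figures:

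- At n = 200 and alpha .05: "we should be able to detect an f^2 of 0.056".
- At n = 160 and alpha .05: "we would still be power enough to detect an f^2 of .070".
- For multiplicity, with up to nine regression models: "we ran our models assuming an alpha of 0.05 / 9", followed by "Based on this reduced alpha, we expect to be able to detect an effect of .07".

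It also interprets the first figure as a share of variance: "the three-way interaction would need to explain an additional 5.6% of the variability to be detected".

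Section 14.1 sets out four conditions, randomised within strata of sex and pubertal stage, and adds: "Pubertal stage will then be treated as a continuous variable". Section 14.4 names Benjamini-Hochberg as the correction that will actually be applied.

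**The concern.** The Bonferroni sentence changes one stated input, alpha, from .05 to .0056. A ninefold cut in alpha should raise the detectable effect substantially, yet the reported value only moves from .056 to .07. The section gives the same .07 for a different change, the loss of 40 participants at the original alpha.

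This is the plan's only statement of what the trial can detect after correction for multiple testing. As written, the correction looks almost free. A reader would credit the corrected test with 80% power at f² = .07 and could take a null corrected result as evidence against effects of that size. If true power is 57% to 66%, the chance of missing such an effect is 34% to 43%, not 20%.

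**Working it through.** **Inputs.** From 14.2: n = 200 (or 160), alpha = .05 or .05/9 = .00556, power .80, 12 covariates. From 14.1: four conditions (3 df), sex (1 df), continuous pubertal stage (1 df). The three-way term therefore has u = 3 × 1 × 1 = 3 df. The full model has main effects 3 + 1 + 1 = 5, two-way terms 3 + 3 + 1 = 7, the three-way term 3 and covariates 12, in total 27 predictors. Error df is v = 200 − 27 − 1 = 172, or 132 at n = 160. The values of u and v are inferred, because equation 1, which 14.2 cites, is not in the document.

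**Method.** Power = P[F′(u, v, λ) > F(1 − alpha; u, v)], where F′ is noncentral F. Solve for the λ that gives power .80, then convert it to f². Two conventions are in play: λ = N·f², and the pwr rule λ = f²·(u + v + 1).

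**Required λ (u = 3, v = 172).** It is 11.15 at alpha .05 and 17.69 at alpha .05/9. The ratio is 17.69/11.15 = 1.59, whichever convention is used. Dividing by N = 200 gives .0558 and .0884. Dividing by u + v + 1 = 176 gives .0634 and .1005.

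**The plan's own figures first, then the disputed one:**

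| Setup (u = 3) | n = 200, alpha .05 | n = 160, alpha .05 | n = 200, alpha .05/9 | Power at f² = .07, alpha .05/9 |
|---|---|---|---|---|
| Plan | .056 | .070 | .07 | 80% (implied) |
| λ = N·f², 27 predictors | .0558 | .0702 | .0884 | 65.6% |
| pwr rule, v = n − 4 | .0556 | .0699 | .0880 | 65.9% |
| pwr rule, 27 predictors | .0634 | .0826 | .1005 | 57.3% |

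The two middle rows return both alpha-.05 figures in the plan, and both put the Bonferroni figure at .088. The last row is pwr applied to the full model as 14.2 describes it. In that row the plan's .056 and .070 would be .063 and .083.

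**Check that does not depend on the inferred df.** The ratio of detectable f² at alpha .05/9 to that at alpha .05 (v = 172) is:

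| u | 1 | 2 | 3 | 4 | 9 | 15 | 27 |
|---|---|---|---|---|---|---|---|
| Ratio | 1.683 | 1.617 | 1.586 | 1.566 | 1.522 | 1.502 | 1.484 |

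The plan's ratio is .07/.056 = 1.25. With the most favourable rounding it is .0749/.0555 = 1.35. Neither reaches 1.484. Applying the 3-df ratio to the plan's own value gives .056 × 1.586 = .089.

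**Attempts to rescue .07.**

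- Unlimited error df (v = 10,000, λ = N·f²): detectable f² is .0853, and power at .07 is 68%.
- Reading .07 as high as .0749: power is 70% (N·f²) or 62% (pwr, v = 172).
- Reading .07 as a partial R², so f² = .07/.93 = .0753: power is 62% to 71%.
- A 1-df test: .067 to .077 at alpha .05/9, but only .040 to .046 at alpha .05, and a four-condition interaction does not have 1 df.
- A 2-df test with 27 predictors under pwr: .056 at alpha .05, but .073 at n = 160 and .091 at alpha .05/9.
- Alpha at which .07 has 80% power with u = 3, v = 172: about .0195 (.05/2.6) under N·f², or .034 (.05/1.5) under the pwr rule.

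**Variance share.** f² = ΔR²/(1 − R² of the full model). The full R² is at least ΔR², so ΔR² ≤ f²/(1 + f²) = .056/1.056 = .053. The interaction would explain at most 5.3% of total variability, not 5.6%.

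**The case against.** The strongest reply concerns weight. Section 14.4 plans Benjamini-Hochberg, which the plan itself describes as more powerful than Bonferroni, and nine models is an upper bound. Section 14.3 names two outcomes. If the family were only their two three-way tests (an assumption, since the plan does not define the family), alpha would be .025. The detectable f² would then be .066 with 83% power at .07 under N·f², or .075 with 76% under pwr with v = 172. So 57% to 66% is not the power of the procedure that will be run. This stands and limits the seriousness. It does not rescue the sentence, which says the models were run at .05/9. A Bonferroni figure offered as the conservative case fails its purpose if it is too favourable.

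A second reply is that the Bonferroni sentences do not restate the three-way term, the 80% power or the f² unit, so both figures need not describe the same test. That is formally true. No different test or power is stated, however, and the only test found to come near .07 has 1 df.

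A third point is fair. Figures of .10 and 57% belong to a setup in which .056 would itself be .063, so strictly the values consistent with .056 are .088 and 66%. The documents also cannot show how .056 and .070 were obtained. An N·f² rule with the full model and a pwr run that left the covariates and lower-order terms out of the error df reproduce them equally well. The second would sit badly with the claim that 12 covariates were allowed for. The sponsor should check which was done.

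**Conclusion.** The concern holds. The detectable f² of .056 at alpha .05 and .07 at alpha .05/9 are incompatible for any single test with numerator df from 1 to 27 (computed at error df 172). Taking .056 as given, the Bonferroni figure is about .088, with about 66% power at .07. Applying the named package to the full model, it is about .10, with 57% power at .07. These sizes rest on u = 3 and 27 predictors, inferred from the design. The incompatibility itself does not rest on them.

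The error is moderate. It affects the only detectable-effect statement that allows for multiplicity, but not the sample size, the randomisation or the planned correction. Every candidate value remains between Cohen's small (.02) and medium (.15), as the section says. The 5.6% wording is a separate, minor slip.

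**What to change.** In section 14.2:

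1. Re-run the power calculation and state the numerator df, the error df and the noncentrality rule.
2. Replace .07 in the Bonferroni sentence, name the unit as f², and use one convention for all three figures. With the df inferred here, the sets are .056 / .070 / .088 (N·f²) or .063 / .083 / .10 (pwr, full model). If a divisor other than nine was intended, say so.
3. Replace the 5.6% statement with f² = .056 relative to unexplained variance, which is at most 5.3% of total variability.

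The cost is one to three numbers and a sentence or two of wording. Sample size, randomisation, the nine-model upper bound and the analysis can stay as they are.

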Background Aim 3: To examine the emergence of sex differences in social buffering effectiveness with puberty. Basal cortisol levels increase from childhood to adolescence as does HPA reactivity to social evaluative stressors (van den Bos et al., 2016). These changes are related to pubertal stage (Adam, 2006). Sex differences in the cortisol response to social evaluative stressors are not consistently observed until later in puberty when, similar to adults, males elevate salivary cortisol more to these stressors (e.g., Bouma et al., 2009). Among adults, the patterns of sex differences in HPA axis functioning are complex, and are reflected in some but not all measures (Kudielka & Kirschbaum, 2005). Notably, the larger cortisol response for men is found in salivary (free/unbound) cortisol but not total cortisol. Women in the luteal phase of their cycle showed similar cortisol levels to men, but not women in follicular phase (Kudielka & Kirschbaum, 2005). Thus, it is likely that this finding relates to estrogen and progesterone influences on cortisol binding globulin, and not to reactivity of the axis, per se. Nonetheless, as girls begin to cycle more regularly and produce increased levels of

Social buffering is an example of received support. Often there is one person who is being stressed and another who is providing support. Received support can backfire if the support person evaluates the support recipient or acts in a way that makes the recipient feel less competent (Uchino, 2009). Giving support also relieves stress and perhaps enhances one's sense of competence (Eisenberger, 2013).

Teens are strongly motivated to

PROTOCOL TITLE: Does Social Buffering Continue to be Effective Over the Peripubertal Period
When Friends Share the Stressor Experience?

VERSION DATE: v.3.3 3.31.23

estrogen and progesterone across the cycle, we might expect to see similar variations in salivary (free) cortisol levels and reactivity. Therefore, we will have girls report on the date of their last period and whether their periods are regular. We can use these data if we find sex differences in cortisol reactivity.

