4.2 Drug/Device Handling: NA

4.3 Biosafety: NA

4.4 Stem Cells: NA

5.0 Procedures Involved

PROTOCOL TITLE: Does Social Buffering Continue to be Effective Over the Peripubertal Period
When Friends Share the Stressor Experience?

VERSION DATE: v.3.3 3.31.23

5.1 Study Design: **Rationale:** Adolescents experience social evaluation stress frequently. However, it is likely that often they are not alone, but with friends who are also going through the same experience. Thus, it is possible that under these conditions, social buffering by friends does not wane over the peripubertal period. Participants will be assigned to social conditions while engaging in an evaluative stressor task.

All sessions will occur ONLINE in a modification to accommodate COVID-19.

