Stressor Paradigm: TSST paradigm with the child facing a camera and two judges (one male, one female). After consent, parents are invited to exit the call (or leave the room); in our recent experience with a Zoom'd TSST, youth and parents readily agreed to this separation. A period of 'rest' begins where youth watch approximately 20-25 minutes of a mildly amusing child appropriate animated movie. The experimenter then sends them to a breakout room to begin the TSST sequence. They are greeted by 2 "judges", given instructions for the speech and told that they have 5 min to prepare. During that time, the judges turn off their audio/video but clearly remain in the breakout room. When 5 minutes elapse, the judges reappear. If the condition is one of support, the Peer or Friend is sent back to the main room and either released from the call or told to continue preparation for another 10 minutes until it is their turn. The judges give final speech instructions, and tell the youth to begin their speech, and then transition to the math. That participant is then excused back to the main room. If the condition calls for a Peer or Friend to perform the TSST, they are then sent to the judging breakout room and deliver their speech/math. After each participant completes the speech/math, they return to the main room and are greeted by the friendly experimenter, who guides them through REDCap links to the various surveys. At several points in session 2, saliva samples are obtained.

Note: In all conditions, one participant will be the target, even though in two of the conditions (Close Friends and Unfamiliar Peer Both Tested), both youth will go through the TSST and all physiological measures will be obtained. The reason for this is two-fold: (1) when we recruit we will know

PROTOCOL TITLE: Does Social Buffering Continue to be Effective Over the Peripubertal Period
When Friends Share the Stressor Experience?

VERSION DATE: v.3.3 3.31.23

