MacArthur Health and Behavior Questionnaire (HBQ) for 9-18 Year-Olds (Parent and Child, 2.1): This questionnaire was developed by Marilyn Essex based on the original HBQ for 4-8 year olds. We have used it many times. The scales we proposed to use here have high reliabilities (Cronbach

PROTOCOL TITLE: Does Social Buffering Continue to be Effective Over the Peripubertal Period
When Friends Share the Stressor Experience?

VERSION DATE: v.3.3 3.31.23

alpha's > .8). We will use the peer scales (acceptance/rejection, bullied, relational victimization, asocial, behavioral inhibition) and broad-band symptoms scales (Internalizing, Externalizing). These measures will be examined for balance across groups and if differences by condition, pubertal stage, or sex are found, will be entered as covariates.

Self-Report of Stress: As a manipulation check, participants will rate their arousal and emotional state at various points during each study using Likert-type scales

Version 2.0 addition: Added Child-self-report RSQ for Peer, Family, & Academic Stress, and PALS Student report of adaptation to challenge in environment.

Physiological Measures.

Stress Hormones: We will assay saliva samples for stress sensitive hormones: **cortisol** and **alpha-amylase**. Saliva will be collected using SalivaBio Oral Swabs (SOS) or passive drool and stored frozen at -30°C until shipped for assay. All testing will be conducted in the late afternoon to control for circadian rhythm. Medications will be recorded from parent report and classes of drug codes will be used to group meds by presumed mechanisms of action and will be entered as covariates (Granger et al., 2009). Systemic glucocorticoid medications are an exclusion criterion. For each analyte, we will calculate area under the curve from intercept (AUCi) to provide a single measure for the main analysis.

- 5.3 Study Duration: Participants will attend two sessions. Session 1 will be 1-1.5hr; Session 2 will be 2-2.5 hrs. It is expected that it will take approximately 2 years to enroll all study participants, and that the study will end, including data analyses, approximately 5 years after enrollment begins.

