14.3 Statistical Analysis: The primary analyses will consist of a series of multiple regression models. For each dependent variable, Cortisol AUCi, Alpha-Amylase AUCi, we will begin by testing the three-way interaction between social buffering condition, sex, and pubertal stage for all outcomes. If the three-way interaction is not significant, we will then examine all two-way interactions. If the two-way interactions are not significant, we will then examine main effects only models. If the three-way interaction is significant, we will not examine any other model.

14.4 Data Integrity: *Multiplicity of testing.* We will correct for multiple comparisons using the Benjamini-Hochberg (BH) correction. The BH method works by controlling the false discovery rate, and relative to the Bonferroni's correction is more powerful, while still adequately protecting against Type I errors (Williams et al., 1999).

Missing data. If there is missingness in any of the dependent or independent variables, multiple imputation will be used (Little & Rubin, 2014; Peng et al., 2006; Schafer & Graham, 2002). Variables related to the missingness and the variables missing data will be included in the missing data model. In the event that missingness is not at random (MNAR), we will investigate the use of models for non-ignorable missing data.

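### The AUCi models do not prespecify adjustment for each analyte's own starting level, and the covariate screen could drop it, so a likely but unquantified gain in precision is left to chance

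*Combined protocol and SAP*

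**What the plan says.** Section 5.2 (Stress Hormones) reduces each analyte to one number: "For each analyte, we will calculate area under the curve from intercept (AUCi) to provide a single measure for the main analysis". Section 14.3 then regresses it: "For each dependent variable, Cortisol AUCi, Alpha-Amylase AUCi, we will begin by testing the three-way interaction between social buffering condition, sex, and pubertal stage". If the three-way term is not significant, the models step down to two-way interactions and then to main effects.

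Covariates are chosen by the screen in section 14.1: "Those covariates that are associated with the independent and outcome variables will be controlled for in the primary analyses". The independent variables for this purpose are condition, sex and pubertal stage. Variables that fail the screen only describe the sample and, in the plan's words, "will not need to be included in the analyses to obtain unbiased estimates".

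Section 5.2 names relationship quality, the HBQ scales and medication classes as possible covariates. The full candidate list is placed "in section 4.3, Outcome Variables", but section 4.3 of this document reads "4.3 Biosafety: NA". Section 14.2 also points to an equation 1, which is not in the available text.

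On sampling, section 5.2 says only: "At several points in session 2, saliva samples are obtained". Section 2.3 (Background Aim 3) notes: "Basal cortisol levels increase from childhood to adolescence as does HPA reactivity to social evaluative stressors".

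**The concern.** AUCi is a change score: total area minus the intercept value times the duration. It removes the starting level with a weight of one, whatever the actual relation between starting level and response. Putting the intercept value in the model lets the data set that weight. The condition coefficients are then identical to those from an ANCOVA on total area.

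The screen asks only whether a covariate is needed to avoid bias. Under randomisation a baseline is expected to be unrelated to condition, and its usual value is that it predicts the outcome. A rule that requires association with an independent variable as well can discard a variable of exactly that kind. Whether starting cortisol or starting sAA enters its model would then depend on the data and could differ between the two outcomes.

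What is at stake is residual variance in the condition tests. The three-way test matters most, because its result decides which models are examined next.

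**Working it through.** **Inputs from section 14.2.** N = 200, α = .05, power .80, 12 covariates, minimum detectable f² = .056 for the three-way interaction, and .070 at N = 160.

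**Reproducing the plan's figure.** With four conditions, sex and continuous pubertal stage, the design terms are 3 + 1 + 1 main effects, 3 + 3 + 1 two-way terms and 3 three-way terms, 15 in all. The tested block has u = 3. Residual df are v = 200 − 12 − 15 − 1 = 172. A noncentral F with λ = f²·N gives a minimum detectable f² of 0.0558 at N = 200 and 0.0702 at N = 160 (v = 132), which match. The convention of the pwr library, λ = f²·(u + v + 1), gives 0.0634 and 0.0826 with the same v. On that convention power at f² = .056 is 74.4%. Both are carried below. The gap between 80% and 74% comes from the convention and has nothing to do with the baseline.

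**Variance saved.** Let B be the intercept value, Y the total area divided by duration, r their correlation and k = SD(Y)/SD(B). In units of Var(B):

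- AUCi alone: k² + 1 − 2rk
- AUCi adjusted for B: k²(1 − r²)
- saving as a share of the first: (1 − rk)² / (k² + 1 − 2rk), which is zero when rk = 1

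The documents give neither r nor k, so both are assumed. Example at k = 1, r = .3: 0.91 / 1.40 = 0.65. The ratios of adjusted to unadjusted residual variance are:

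| k | r = .3 | r = .5 | r = .7 |
|---|---|---|---|
| 1 | 0.65 | 0.75 | 0.85 |
| 1.25 | 0.78 | 0.89 | 0.98 |
| 1.5 | 0.87 | 0.96 | 1.00 |

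The cut therefore runs from about 0% to 35%.

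**Power.** The added covariate leaves v = 171. An effect of f² = .056 on the unadjusted scale becomes .056/(variance ratio):

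| Variance cut | λ = f²·N | pwr convention |
|---|---|---|
| 0% | 80% | 74% |
| 10% | 85% | 79% |
| 15% | 87% | 81% |
| 25% | 91% | 86% |

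**Worst case.** With no variance saved, the lost df moves power from 80.18% to 80.18% (no visible change) on the first convention and from 74.4% to 74.1% on the second, so at most about 0.3 points.

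**The case against.** Four objections carry weight.

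*The baseline may already be a candidate.* A reader might infer from the named covariates that the starting level is never adjusted for. The documents do not show that. The candidate list and the model equation are not in the available text, and if starting cortisol is a candidate it could pass the screen through pubertal stage, given the background statement on basal cortisol. Only the absence of prespecification can be shown.

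*The gain is not assured.* It is also tempting to say that adjustment would sharpen every condition test. The variance table includes ratios of 0.96, 0.98 and 1.00, where almost nothing is gained, and cortisol and sAA may differ. The gain is possible, and its size is unknown.

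*The intercept sample may be affected by condition.* Sampling times are not listed, and in session 2 the friend or peer joins online. AUCi already subtracts this sample, so any effect of condition on it already reaches the planned outcome. But conditioning on an affected variable is a different operation from subtracting it and changes what is estimated. This stands, and it limits the fix.

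*Sex and pubertal stage are not randomised.* If basal cortisol differs by puberty, adjustment turns their own terms from reactivity into reactivity at equal baseline. This stands too.

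**Conclusion.** The point holds as one of efficiency. The primary AUCi models do not prespecify the analyte's starting level, and the screening rule would leave out a baseline that is only prognostic. On the assumed ranges of r and k the saving is 0% to 35% of residual variance. At f² = .056, a cut of 10% to 25% is worth about 5 to 11 power points under the convention that matches the plan (80% to 85% and 91%) and about 5 to 12 under the pwr convention (74% to 79% and 86%).

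A reader might take this to mean that the planned condition comparisons are biased. The documents do not support that: condition is randomised within sex-by-puberty strata, so unadjusted AUCi remains a valid comparison, and the baseline is already used through the subtraction. The change is worth making because its statistical cost is negligible, provided the timing of the intercept sample is settled first.

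**What to change.** In section 14.3:

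1. Prespecify the analyte's own intercept value (cortisol for cortisol AUCi, sAA for sAA AUCi) as an always-included covariate for all tests involving condition, exempt from the section 14.1 screen.
2. State that the intercept sample is the one taken before the partner joins or the task is announced. If it is taken later, keep unadjusted AUCi as primary and report the adjusted model as a sensitivity analysis.
3. Report the sex and pubertal-stage terms that do not involve condition without baseline adjustment as well, noting that the adjusted versions describe reactivity at equal baseline.

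In section 5.2, list the session 2 saliva sampling times so that item 2 can be checked.

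The cost is a few sentences, one df per model, a second report of the non-randomised terms and the change in their interpretation. No new data are needed, since every target with an AUCi has the intercept value.

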
1.0 Objectives

1.1 Purpose: The purpose of this experiment is to determine whether social buffering by friends of stress physiology remains effective later in puberty when friends share the load versus when they provide support but are not undergoing the stressor with the target child. There are four conditions: (1) Friend and Target both undergo the stressor, (2) Friend provides support but does not undergo the stressor, (3) Unfamiliar Peer and Target undergo the stressor, and (4) Alone (no partner).

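### Section 14.3 specifies no late-puberty condition contrast, and when no interaction is significant it falls back on a model that cannot answer the trial's stated question

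*Combined protocol and SAP*

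**What the plan says.** Section 1.1 (Purpose) asks "whether social buffering by friends of stress physiology remains effective later in puberty when friends share the load", compared with a friend who supports the target without being tested. The rationale in section 5.1 adds that "it is possible that under these conditions, social buffering by friends does not wane over the peripubertal period". The background in section 2.3 predicts opposite directions for the two friend conditions: less stress responding when both friends are tested, more when one friend only supports.

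Section 14.1 plans 100 girls and 100 boys as targets. "Within each group there will be 50 early and 50 late puberty participants". Then "participants within a group will be randomly assigned to one of four conditions equally in order to have a balanced design". For the analysis, "Pubertal stage will then be treated as a continuous variable".

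Section 14.3 gives an order of model fitting for cortisol AUCi and alpha-amylase AUCi. The condition × sex × puberty interaction is tested first. If it is significant, no other model is examined. If it is not, the two-way interactions follow. "If the two-way interactions are not significant, we will then examine main effects only models".

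In the text available, section 14.3 names no contrast between conditions, no effect or slope at late puberty, no confidence interval and no margin. Section 14.2 refers to an equation 1 that does not appear, and nothing here relies on it. Section 3.2 lists the two analytes as primary; its only mention of later puberty is an exploration of sex differences.

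**The concern.** The purpose names a quantity: the difference in stress response, later in puberty, between friends who are both tested and the relevant comparators. The planned sequence commits to estimating it on none of its paths. If an interaction is significant, no follow-up estimate at late puberty is prescribed. If none is, the final model has no condition × puberty term, so it gives one condition effect averaged over stage. Because stage is stratified as early or late but modelled as continuous, later puberty also has no defined value at which to evaluate anything.

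At stake is the conclusion about the stage the trial is about. Suppose the shared-stressor condition buffers in early puberty and not at all late. The interaction test may well miss this. The report would then contain either a pooled effect that is wrong for late puberty or a null pooled result that is silent on it. Either way the key comparison would have to be chosen after the data are seen.

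**Working it through.** **The plan's own figure.** Section 14.2 states a minimum detectable f² of 0.056 for the three-way interaction (n = 200, alpha 0.05, power 0.80, 12 covariates). With four conditions the term has 3 df. The full model has 15 design terms and 12 covariates, so the error df are 200 − 15 − 12 − 1 = 172. With noncentrality λ = f² × N = 0.056 × 200 = 11.2, power is 0.802. The same method gives 0.070 at n = 160. Both stated figures reproduce. (The cited package's own noncentrality convention with 172 error df would give 0.063; the point here does not turn on that.)

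**Inputs for the check.** From section 14.1: 200 targets, half early and half late, four equal conditions, so 200 / (4 × 2) = 25 per condition and stage. Assumed: unit SD, two-sided 0.05, no covariates, no multiplicity correction, and buffering in the friend-both-tested condition only, of size d early and 0 late. The documents give no value for d, so a range is shown.

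**Formulas.**
- Interaction contrast (friend-both-tested minus no partner, early minus late): SE = √(4/25) = 0.40 SD, 95% half-width 1.96 × 0.40 = 0.78 SD.
- Condition × puberty test on 3 df: the change is d in one condition and 0 in three, so the squared deviations sum to 0.75d². Then λ = 0.75d² / (2/25) = 9.375d².
- Pooled contrast over stage: true value d/2, SE = √(2/50) = 0.20 SD.
- Late-puberty contrast, 25 v 25: SE = √(2/25) = 0.283 SD, half-width 0.55 SD.

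**How often complete waning is missed.**

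| d | 1-df contrast | 3-df test | Neither three-way nor condition × puberty significant (simulated, 4,000 runs) |
|---|---|---|---|
| 0.3 | 88% | 90% | 85% |
| 0.5 | 76% | 78% | 75% |
| 0.8 | 48% | 49% | 47% |
| 1.0 | 30% | 28% | 26% |

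The 1-df contrast needs d = 1.12 for 80% power. Read as a condition × puberty effect, the plan's f² of 0.056 (λ = 11.2) corresponds to d = √(11.2/9.375) = 1.09: the loss of an effect of about 1.1 SD in one condition. With an assumed five-level stage score and a linear decline, the simulated miss rate rises to 83% at d = 0.5, 70% at 0.8 and 55% at 1.0.

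**How often the misleading path occurs.** In this layout the pooled contrast has the same z as the interaction contrast (0.5d/0.20 = d/0.40) and is independent of it. The chance of a non-significant interaction with a significant pooled contrast is therefore (1 − power) × power:
- d = 0.5: 0.76 × 0.24 = 18%
- d = 0.8: 0.48 × 0.52 = 25%
- d = 1.0: 0.30 × 0.70 = 21%

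Simulating the whole sequence with all two-way interactions and the 3-df condition test (20,000 runs) gives 14%, 21% and 17%. At d = 0.5 the commonest outcome by the contrast calculation is that neither is significant: 0.76 × 0.76 = 58%.

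**The case against.** **No interpretation rule is stated.** A reader might infer that the plan treats a non-significant interaction as proof that buffering does not wane. It does not say so. Section 14.3 gives only an order of fitting, and section 5.1 calls the absence of waning possible, no more. This stands. What remains is that the plan leaves the reading open and offers no estimate in its place.

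**The predicted pattern can be supported by rejection.** If sharing continues to buffer while support alone turns counter-productive, condition × puberty is not null. For example, with sharing at −0.5 SD at both stages and support moving from −0.5 to +0.5 SD, the 3-df test has 72% power. This is a fair point, so the hypothesis does not rest only on failing to reject. But if support merely falls to zero, power is 22%. And a significant 3-df test says neither which conditions differ late nor in which direction, so the contrast is still needed.

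**The miss rate depends on d.** A reader might carry away three misses in four as a property of the design. It belongs to d = 0.5 only. At an effect as large as the plan's own f² of 0.056, about one in five is missed.

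**The misleading pooled claim is not the usual outcome.** At d = 0.5 the trial more often finds nothing significant. That avoids a false claim about late puberty but does not answer the question either.

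**Conclusion.** The mismatch holds on the text alone: section 1.1 asks about late puberty, and the sequence in section 14.3 does not commit to estimating anything there. The main-effects-only fallback cannot do so.

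The size depends on assumptions the documents do not settle. With 25 per condition and stage, unit SD, and waning confined to the friend-both-tested condition, the interaction test misses complete waning in about nine trials in ten at d = 0.3 and about three in ten at d = 1.0. The early/late split is favourable: a spread-out stage score would usually lower power, and so would the Benjamini-Hochberg correction in section 14.4. The path that would misstate late puberty arises in roughly 14–25% of trials for d between 0.5 and 1.0. That is material, but it is not the most likely result. The documents do not support saying that the plan equates non-significance with no waning.

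**What to change.** In section 14.3, and in section 3.2, prespecify for cortisol AUCi two model-estimated differences:
- friend-both-tested minus no partner;
- friend-both-tested minus friend-supports.

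Evaluate each at a stated late-puberty value of the continuous stage score, from the model that contains condition × puberty. Report both with 95% confidence intervals whatever the interaction tests show.

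Add three sentences on interpretation. A late-puberty interval that excludes zero in the buffering direction supports the statement that buffering remains effective later in puberty. A non-significant interaction is not evidence of no waning. Any claim that buffering does not wane must rest on the confidence interval for the change in the contrast across puberty, set against a stated margin. A late interval that excludes zero is not enough for that last claim: a fall from 1.2 to 0.6 SD could pass.

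The cost is wording and two contrasts from a model already planned, with no new data or participants. The drawback is precision. The late-puberty intervals will be about ±0.55 SD, and power for a late effect of 0.5 SD is 42%. The change yields the right estimate and shows openly how little the sample can say about it.
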